6.2.6.2. Adverse Reactions from Clinical Trials

The presentation of adverse reactions identified from clinical trials is the major component of the Adverse Reactions section. The Adverse Reactions section must include a listing of all such reactions that occurred at or above a specified rate that is appropriate to the drug's safety database, a separate listing of those adverse reactions that occurred below the specified rate, but for which there is some basis to believe there is a causal relationship between the drug and the event, and, to the extent information is available and relevant, additional detail about the nature, frequency, severity, duration, dose-response, and demographic characteristics of those adverse reactions with significant clinical implications.

The following is the recommended organization of adverse reactions identified from clinical trials.

- Adverse Reaction (21 CFR 201.57(c)(7)): An adverse reaction is an undesirable effect, reasonably associated with the use of a drug, that may occur as part of the pharmacological action of the drug or may be unpredictable in its occurrence. This definition does not include all adverse events observed during use of a drug, only those for which there is some basis to believe there is a causal relationship between the drug and the occurrence of the adverse event. Adverse reactions may include signs and symptoms, changes in laboratory parameters, and changes in other measures of critical body function, such as vital signs and ECG.
- Adverse Event (or adverse experience): The term adverse event refers to any untoward medical event associated with the use of a drug in humans, whether or not considered drug-related.

- **Serious Adverse Reaction:** The term serious adverse reaction refers to any reaction occurring at any dose that results in any of the following outcomes: death, a life-threatening adverse experience, inpatient hospitalization or prolongation of existing hospitalization, a persistent or significant disability or incapacity, or a congenital anomaly or birth defect. Important medical events that may not result in death, be life threatening, or require hospitalization may be considered serious adverse reactions when, based upon appropriate medical judgment, they may jeopardize the patient or subject, and may require medical or surgical intervention to prevent one of the outcomes listed in this definition.

6.2.6.3. Classification of Adverse Events

Adverse events are to be recorded on the AE page of the subject's case report form (CRF). Severity will be graded according to the following definitions:

- **Mild:** The subject experiences awareness of symptoms but these are easily tolerated or managed without specific treatment.
- **Moderate:** The subject experiences discomfort enough to cause interference with usual activity, and/or the condition requires specific treatment.
- **Severe:** The subject is incapacitated with inability to work or do usual activity, and/or the event requires significant treatment measures.

Action taken will be categorized as none, study drug discontinued, dose modified, required concomitant medication, required procedure, or other.

Event outcome at resolution or time of last follow-up will be recorded as event resolved, resolved with sequelae, ongoing, or death.

6.2.6.4. Causality/Drug Relationship Assessment

The relationship of the event to the study drug should be determined by the investigator according to the following criteria: **Definitely related:** The event follows a reasonable temporal sequence from the time of drug administration that cannot be explained, follows a known or expected response pattern to the study drug, that is confirmed by improvement on stopping and reappearance of the event on repeated exposure and that could not be reasonably explained by other factors such as the subject's clinical condition, intercurrent illness, or concomitant drugs.

- **Definitely related:** The event follows a reasonable temporal sequence from the time of drug administration that cannot be explained, follows a known or expected response pattern to the study drug, that is confirmed by improvement on stopping and reappearance of the event on repeated exposure and that could not be reasonably explained by other factors such as the subject's clinical condition, intercurrent illness, or concomitant drug.
- **Probably related:** The event follows a reasonable temporal sequence from the time of drug administration, and/or follows a known response pattern to the study drug, and cannot be reasonably explained by other factors such as the subject's clinical condition, intercurrent illness, or concomitant drugs.

- **Possibly related:** The event follows a reasonable temporal sequence from the time of drug administration, and/or follows a known response pattern to the study drug, but could have been produced by other factors such as the subject's clinical condition, intercurrent illness, or concomitant drugs.
- **Unlikely related:** The event follows little or no temporal sequence from the time of drug administration that makes a causal relationship improbable and/or other factors such as the subject's clinical condition, intercurrent illness, or concomitant drugs is a more likely alternative.
- **Not related:** The event is most likely produced by other factors such as the subject's clinical condition, intercurrent illness, or concomitant drugs, and does not follow a known response pattern to the study drug, or the temporal relationship of the event to study drug administration makes a causal relationship unlikely.

6.2.6.5. Actions Taken for SAE

Actions taken may consist of:

- None: No action taken
- Treatment: Standard of care measures instituted
- Drug withdrawn: Study medication was permanently discontinued because of the AE
- Unknown: Not known, not observed, not recorded, or refused

6.2.6.6. Outcome at the Time of Last Observation

The outcome at the time of last observation will be classified as:

- Recovered/resolved
- Recovered/resolved with sequelae
- Not recovered/not resolved
- Death
- Unknown

6.2.6.7. Definition of Serious Adverse Events

A serious AE (SAE) is any AE that fulfills any of the following criteria, as per 21 CFR 312.32:

- Results in death;
- Is life-threatening;
- Requires in-patient hospitalization or prolongation of existing hospitalization;
- Results in persistent or significant disability or incapacity;
- Is a congenital anomaly or birth defect;

- Is medically significant or requires intervention to prevent one of the outcomes listed above.

Serious AEs will be captured from the time of consent through the end of the study

6.2.6.8. Adverse Event Recording and Reporting

Adverse events will be recorded throughout the study in the source documents and in the CRFs.

If known, the diagnosis should be recorded, in preference to the listing of individual signs and symptoms. Adverse event reporting for each subject starts when the subject signs the informed consent and continues at all subsequent visits through the Follow up Visit. Any preexisting conditions that are detected as part of the screening procedures will need to be reported in the medical history and not as an AE.

The investigator will rate AEs for seriousness, intensity, causality, action taken, and outcome as described in the previous sections.

Expedited reporting is required for serious unexpected adverse drug reactions. Fatal or life-threatening unexpected drug reactions must be reported by the Sponsor to regulatory agencies no more than 7 days after the Sponsor's first knowledge of the reaction; followed by as complete a report as possible within 8 additional days. Unexpected drug reactions must be reported no later than 15 days after the Sponsor's first knowledge of the reaction. In order to comply with these requirements, the investigator or delegate must inform the Sponsor immediately upon occurrence of any SAE. The site will complete the SAE Report Form as thoroughly as possible and fax it to Insys within 24 hours of the investigators first knowledge of the event.

Sponsor contact information is listed below:

[REDACTED]
[REDACTED]
Insys Development Company, Inc.

Email: [REDACTED]

Telephone: [REDACTED]

These SAE reports must contain the following information:

- A. Study name/number
- B. Study drug
- C. Investigator details (name, phone, fax, e-mail)
- D. Subject number
- E. Subject initials
- F. Subject demographics
- G. Clinical event
 - 1) Description
 - 2) Date of onset

- 3) Treatment (drug, dose, dosage form)
 - 4) Adverse event relationship to study drug
 - 5) Action taken regarding study drug in direct relationship to the AE
- H. If the AE was fatal or life-threatening
- I. Cause of death (whether or not the death was related to study drug)
- J. Autopsy findings (if available)

The Sponsor or its representative will be responsible for notification to regulatory agencies.

6.2.6.9. Adverse Event Follow-Up

All non-serious AEs that are not related or unlikely to be related to study treatment will be followed until the end of study participation. All SAEs or AEs that are considered as possibly, probably, or definitely related to treatment will be followed until resolution or stabilization.

6.2.6.10. Special Considerations

Pregnancy

All women of childbearing potential who participate in the study should be counseled on the need to practice adequate birth control and on the importance of avoiding pregnancy during study participation. Women should be instructed to contact the investigator or study staff immediately if pregnancy occurs or is suspected.

Pregnancy testing will be conducted before IP administration on every woman of childbearing potential. A woman who is found to be pregnant at the Screening Visit will be excluded from the study and considered to be a screening failure.

If a subject becomes pregnant, the investigator must report the pregnancy within 24 hours of learning of the pregnancy. The investigator should contact the designated individual(s) who receive SAE notification and record information related to the pregnancy on the designated form.

The investigator is responsible for following the pregnancy until delivery or termination. These findings must be reported on the designated form and forwarded to the designated individual(s). The event meets the SAE criterion only if it results in a spontaneous abortion or a congenital anomaly.

Subjects who become pregnant during the course of the study will be followed to collect data on lactating women and health of the child (for births) or until termination of the pregnancy.

7. STUDY PROCEDURES

The assessments and procedures that will be conducted during this study are summarized in Table 2.

7.1. Screening (Day -28 to Day -1)

The subject will be screened within 28 days before the scheduled surgery. The following procedures will be performed at Screening:

1. Obtain written informed consent.
2. Review inclusion/exclusion criteria.
3. Collect demographic information.
4. Record medical history, including current therapies (eg, prescription and nonprescription medications), and presence of bunion.
5. Perform a physical examination including height, weight, and BMI.
6. Perform an oral cavity examination.
7. Measure vital signs (resting blood pressure, heart rate, respiratory rate, and oral body temperature).
8. Pulse oximetry.
9. Perform clinical laboratory tests (hematology, clinical chemistry, and urinalysis), urine drug screen, and serum pregnancy test (women of childbearing potential only).
10. Perform a 12-lead ECG.
11. Record concomitant medications.
12. Perform podiatric examination and obtain radiograph (a radiograph taken within the previous 6 months will be acceptable).

7.2. Day 0 (Surgery)

Subjects will be admitted to the study site on the morning of the surgery. The following events will occur:

7.2.1. Pre-surgery

1. Collect medical history (changes since screening).
2. Review inclusion/exclusion criteria.
3. Measure vital signs (resting blood pressure, heart rate, respiratory rate, and oral body temperature).
4. Perform a urine pregnancy test and a urine drug screen.
5. Perform an alcohol breathalyzer test.
6. Record concomitant medications.

7. Record AEs.

7.2.2. Surgery and Standardized Regional Anesthesia

Subjects who continue to meet all study entry criteria will undergo a primary, unilateral, first metatarsal bunionectomy with osteotomy and internal fixation under a standardized regimen of regional anesthesia. Regional anesthesia will be established using a popliteal sciatic nerve block, using standardized techniques. The regional anesthesia will be continued postoperatively via a continuous anesthetic infusion (continuous popliteal sciatic block). Subjects may receive supplemental analgesia with ibuprofen and/or an opioid/acetaminophen combination product and/or ketorolac during the continuous infusion period to help control breakthrough pain if the investigator/study site personnel consider the regional anesthetic infusion to offer inadequate pain control or if it becomes nonfunctional. If the regional anesthetic infusion and supplemental analgesia do not control the subject's postoperative pain effectively, then the subject will be discontinued from the study and further treatment will be according to usual standard of care at the investigator's discretion.

Ibuprofen 400 mg will be allowed orally every 4 to 6 hours as needed for pain before the anesthetic infusion (continuous popliteal sciatic block) is discontinued. If the subject is unable to tolerate 400 mg ibuprofen or if there is insufficient pain relief, then subject may receive supplemental analgesia with a hydrocodone/acetaminophen combination. One to two hydrocodone/acetaminophen 5/325-mg tablets may be administered every 4 to 6 hours as needed for moderate to severe pain, up to a daily limit of 8 to 10 tablets. If the subject cannot tolerate the hydrocodone/acetaminophen or if there is insufficient pain relief, then 30 mg ketorolac tromethamine (eg, Toradol®) may be administered intravenously or intramuscularly every 6 to 8 hours as needed for pain. The total daily (24-hour) dosage of ibuprofen medication should not exceed 2400 mg; the total daily dose of acetaminophen should not exceed 3250 mg; and the total daily dose of ketorolac should not exceed 90 mg.

7.3. Treatment Period (Days 1-3)

The treatment period comprises Day 1 (Baseline before dosing) and Day 2 and 3 (48 hours after the first dose of study medication).

7.3.1. Pre-randomization

On Day 1, the regional anesthetic infusion will be discontinued at approximately 3:00 AM. Thereafter, when subjects request pain medication, they will be asked to rate their pain intensity using an 11-point (0-10) Numeric Rating Scale (NRS). During the 9-hour period after discontinuation of the anesthetic block, subjects who experience a pain intensity rating of ≥ 4 on the NRS are eligible to be enrolled in the study. Subjects whose pain intensity ratings do not meet the minimum entry criteria within 9 hours after discontinuation of the regional anesthesia will not be eligible for enrollment and will receive routine postoperative care at the investigator's discretion. Pulse oximetry will be monitored continuously after the procedure as a safety measure.

When a subject's pain meets the pain intensity entry criteria (≥ 4 on the NRS), he or she will be eligible to begin the Treatment Period and will be randomized.

7.3.2. Post-randomization

1. Measure vital signs (resting blood pressure, heart rate, respiratory rate, and oral body temperature) immediately before and 1 hour after the first dose of study drug on Day 0, then immediately before and 1 hour after the 24-hour and 40-hour doses, and at 48 hours.
2. Perform a 12-lead ECG before the first dose of study drug, and then at 90 minutes and 12, 24, and 48 hours after Time 0.
3. Pulse oximetry will be recorded at selected times, including baseline before Time 0 and at 90 minutes and 12, 24, and 48 hours after Time 0 (Tmax).
4. The subject is to record pain intensity (numerical rating scale) in the inpatient subject diary at Baseline before the first dose of study drug (Day 1). Thereafter, the subject is to record pain intensity and pain relief (5-point categorical scale) assessments at the following time points:
 - a. At 2.5, 5, 15, 30, and 45 minutes and 1, 1.5, 2, 3, 4, 5, 6, 7, 8, 12, 16, 20, 24, 32, 40 and 48 hours after Time 0, and immediately before each use of rescue analgesia.
 - b. At Early Withdrawal if a subject discontinues prematurely.
5. Administer the first dose of study drug within 9 hours (\pm 10 minutes) after the anesthetic block has been discontinued when a subject's pain intensity is ≥ 4 on the 11-point (0-10) NRS. Study drug will be administered from Time 0 through 48 hours within 10-minute windows.
6. Start stopwatches as soon as the first dose of study drug is administered. Stopwatches should be discontinued if the subject has not stopped them by the time of the second IP dose or first use of rescue medication (whichever occurs first).
7. Perform an oral cavity examination prior to and one hour after first dose.
8. Record concomitant medications.
9. Record AEs.
10. Subjects will complete a subject's global evaluation of study drug at the end of the treatment period (Day 3) before discharge from the study site or immediately before ET if a subject discontinues prematurely.
11. Dispense outpatient pain medication and an outpatient subject diary before discharge from the study on Day 3 (approximately 72 hours after completion of surgery).

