An electrocardiogram (ECG) will be conducted after surgery but before the first dose of the study drug and serve as a baseline for comparison to subsequent tracings. The time of the NRS assessment before study drug administration is defined as Baseline; the time of administration of the first dose of study drug is defined as Time 0. Study drug will be provided by blinded study personnel in a predefined manner to ensure adequate blinding and appropriate dosing regimens for the active drug and placebo. Subjects should not have anything orally except room-temperature water within 15 minutes of each dose. The Treatment Period will continue through 48 hours after Time 0. Pulse oximetry will be continuously monitored and SpO₂ data will be recorded at select time points including baseline before first dose of study drug and 90 minutes and 12, 24, and 48 hours after Time 0. Additional ECGs will be performed at 90 minutes, 12 hours, 24 hours, and 48 hours after Time 0.

Ibuprofen 400 mg will be allowed orally every 4 to 6 hours as needed for rescue medication after study drug treatment has begun. If subjects are unable to tolerate 400 mg ibuprofen or if there is insufficient pain relief, 30 mg of ketorolac tromethamine (i.e., Toradol®) may be administered intravenously or intramuscularly every 6 to 8 hours as needed for pain. The total daily (24 hour)

dosage of ibuprofen medication should not exceed 2400 mg and ketorolac should not exceed 90 mg.

During the Treatment Period, subjects will be allowed to use assigned study medication for primary rescue medication no more frequently than 4 hours from previous study medication dose and no more than 6 times in a 24-hour period. Subjects will be encouraged to wait for at least 1 hour after the first dose of study drug before receiving rescue medication to allow time for the study drug to exert its pharmacologic effect.

During the Treatment Period, subjects whose pain cannot be adequately managed (in the investigator's opinion) by a combination of study drug and rescue medication, or who develop unacceptable side effects during the study, will be discontinued from further study participation. Their pain will be managed according to usual standard of care at the investigator's discretion.

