3.3. Removal of Subjects from Therapy or Assessment

All subjects will be advised that they are free to withdraw from participation in this study at any time, for any reason, and without prejudice. Every reasonable attempt should be made by the investigator to keep subjects in the study. However, subjects must be withdrawn from the study if they withdraw consent to participate. Investigators must attempt to contact subjects who fail to attend scheduled visits by telephone or other means to exclude the possibility of an AE being the cause of withdrawal. Should this be the cause, the AE must be documented, reported, and followed as described in Section 6.2.6.8. The sponsor reserves the right to request the withdrawal of a subject due to protocol violations or other reasons.

The investigator also has the right to withdraw subjects from the study at any time for lack of therapeutic effect that is intolerable or otherwise unacceptable to the subject, for intolerable or unacceptable AEs, intercurrent illness, noncompliance with study procedures, administrative reasons, or in the investigator's opinion, to protect the subject's best interest.

If one of the following events occur during the Treatment Period, the subject will be discontinued from further study participation:

1. Hypoxia with oxygen saturation $\leq 90\%$ on repeat measurements over 3 minutes, despite stimulation and receiving oxygen 2-4 L/min via nasal cannula.
2. Hypoxia or respiratory depression requiring the use of naloxone for reversal.
3. Need for noninvasive respiratory maneuvers (eg, jaw thrust, bag-valve mask for positive pressure ventilation, etc.) to improve or maintain adequate respiratory status (ventilation and/or adequate oxygen saturation) at any point during the study.
4. Hypotension requiring intervention, as follows:
 - a. If asymptomatic and <80 mm Hg systolic blood pressure on 3 successive repeat measurements over a 15-minute period.

- b. If symptomatic, but >80 mm Hg systolic blood pressure and does not respond to conservative measures such as oral hydration and/or no more than 1 liter of IV fluids (if more than 1 liter of IV fluid is needed and/or if naloxone is administered, the subject will be discontinued from further dosing).

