Oxygen saturation will be monitored continuously and the study team will measure all vital signs (blood pressure, heart rate, respiratory rate, and oxygen saturation) at least every 5 minutes until the AE of hypotension or hypoxia as described above is no longer present.

5. If >8 mg i.v. ondansetron is needed within an 8-hour segment and persistent nausea and/or emesis is present.
6. Pain cannot be adequately managed (in the investigator's opinion) by a combination of study drug and rescue medication, or who develop unacceptable side effects during the study, will be discontinued from further study participation.

Pain will be managed according to usual standard of care at the investigator's discretion.

If a subject is withdrawn before completing the study, the reason for withdrawal and the date of discontinuation will be recorded on the appropriate case report form (CRF). Whenever possible and reasonable, the evaluations that were to be conducted at the completion of the study should be performed at the time of premature discontinuation.

If a subject discontinues the study prematurely, pain intensity, pain relief, and the subject's global satisfaction with study treatment should be assessed and recorded immediately before discontinuation.

Withdrawn subjects will not be replaced. If a substantial number of subjects are withdrawn from the study, then the sponsor will evaluate the need for developing replacement criteria.

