4. TREATMENTS

4.1. Treatments Administered

Eligible subjects meeting all study entry criteria will be randomly allocated in a 1:1:1 ratio to one of the following treatments containing active or placebo administered up to 6 doses per day as shown in the table below:

Table 1: Study Treatment Regimens

Treatment group	Day 1						Day 2					
	Dose 1	Dose 2	Dose 3	Dose 4	Dose 5	Dose 6	Dose 1	Dose 2	Dose 3	Dose 4	Dose 5	Dose 6
100 µg	100 µg	100 µg	100 µg	100 µg	100 µg	100 µg	100 µg	100 µg	100 µg	100 µg	100 µg	100 µg
200 µg	200 µg	200 µg	200 µg	200 µg	200 µg	200 µg	200 µg	200 µg	200 µg	200 µg	200 µg	200 µg
Matching Placebo	P	P	P	P	P	P	P	P	P	P	P	P

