6.2.3. Vital Signs

Vital signs, including blood pressure, heart rate, respiratory rate, and oral body temperature, will be measured after the subject has been in a resting position for 5 minutes. Vital signs will be measured at Screening and before surgery on Day 0. From Day 1 through discharge from the study site, vital signs will be measured immediately before and 1 hour after the first dose of study drug on Day 0, then immediately before and 1 hour after the 24 hour and 40 hour doses, and at 48 hours. Vital signs will also be measured before Early Withdrawal if a subject discontinues.

Height, weight, and BMI will be recorded at Screening.

Pulse oximetry will be measured at Screening and continuously after the procedure for safety, and recorded at the following times: baseline before Time 0, and at 90 minutes and 12, 24, and 48 hours after Time 0 (T_{max}).

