d Vital signs, including blood pressure, heart rate, respiratory rate, and oral body temperature, will be measured after the subject has been in a resting position for 5 minutes. Vital signs will be measured at Screening and before surgery on Day 0 immediately before and 1 hour (±10 minutes) after the first dose of study drug on Day 0, immediately before and 1 hour (±10 minutes) after the 24-hour and 40-hour doses, and at 48 hours (±10 minutes). Vital signs will also be measured before E.T if a subject discontinues.

e Pulse oximetry will be measured at Screening and continuously after the procedure for safety; pulse oximetry will be recorded at selected times (±10 minutes), including baseline before Time 0 and at 90 minutes and 12, 24, and 48 hours after Time 0 (T_{max}).

f An ECG will be performed before the first dose of study drug, and then at 90 minutes (±10 minutes), and at 12, 24, and 48 hours (±10 minutes) after Time 0.

g A serum pregnancy test will be performed at Screening and a urine pregnancy test will be performed before surgery on Day 0. The test results must be negative for the subject to continue in the study.

h A urine drug screen will be collected at Screening and before surgery on Day 0. The test results must be negative for the subject to continue in the study, except in cases where a valid physician's prescription can be verified.

i Radiographs taken within 6 months before Screening will be acceptable.

j Immediately after the anesthetic block is discontinued, subjects will be instructed to request pain medication when they experience pain.

k The subject will record pain intensity (numerical rating scale) in the inpatient subject diary at Baseline before the first dose of study drug (Day 1). Thereafter, pain intensity and pain relief (5-point categorical scale) assessments will be recorded at the following time points (± 5 minutes):

- At 2.5, 5, 15, 30, and 45 minutes and 1, 1.5, 2, 3, 4, 5, 6, 7, 8, 12, 16, 20, 24, 32, 40 and 48 hours after Time 0, and immediately before each use of rescue analgesia.
- At Early Withdrawal if a subject discontinues prematurely.
- l The first dose of study drug will be administered within 9 hours (± 10 minutes) after the anesthetic block has been discontinued when a subject's pain intensity is ≥ 4 on the 11-point (0-10) NRS. Study drug will be administered from Time 0 through 48 hours within 10-minute windows.

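### Scheduled blood pressure has gaps of 23, 15 and 7 hours; at nominal 4-hourly dosing, 6 of 12 doses have no scheduled reading by the next dose to trigger the asymptomatic-hypotension rule, and a cuff reading before each dose is a cheap repair

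*Protocol*

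**What the plan says.** The blood pressure schedule is the same wherever it appears. Protocol Section 7.3.2 item 1 asks for vital signs before and 1 hour after the first dose, "then immediately before and 1 hour after the 24-hour and 40-hour doses, and at 48 hours". Section 6.2.3 has the same times ("then immediately before and 1 hour after the 24 hour and 40 hour doses, and at 48 hours"), as do Table 2 footnote d ("after the 24-hour and 40-hour doses, and at 48 hours") and SAP Appendix 1 footnote d. Neither document schedules a treatment-period blood pressure at any other time. Readings before early withdrawal are event-driven.

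The other scheduled monitoring does not include blood pressure. Oximetry is continuous, and the ECG and recorded SpO2 contacts fall at 90 minutes and 12, 24 and 48 hours.

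Section 3.3 item 4a lists this among the reasons for mandatory discontinuation: "If asymptomatic and <80 mm Hg systolic blood pressure on 3 successive repeat measurements over a 15-minute period". The same section calls for all vital signs "at least every 5 minutes until the AE of hypotension or hypoxia as described above is no longer present", which starts only once an event has been recognised.

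On dosing, Section 4.1 describes treatment "containing active or placebo administered up to 6 doses per day as shown in the table below". Section 3.1 allows study drug "no more frequently than 4 hours from previous study medication dose and no more than 6 times in a 24-hour period". Section 7.3.2 item 5 adds: "Study drug will be administered from Time 0 through 48 hours within 10-minute windows".

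**The concern.** Item 4a covers a state that, by definition, no symptom announces. If oxygen saturation is also normal, neither the oximeter nor the 5-minute checks will reveal it, so a blood pressure reading has to come first. Where none is scheduled, a mandatory stopping rule depends on someone choosing to take one, and staff can give further opioid doses in the meantime.

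There is a smaller consequence for the data. Safety against placebo is a secondary objective and change in vital signs is a safety endpoint. SAP Section 8.2.9 tabulates vital signs by time point, yet it will have no scheduled blood pressure between 1 hour and the reading before the 24-hour dose. At nominal timing that reading comes about 4 hours after the preceding dose.

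The point is limited to blood pressure. No discontinuation rule uses a respiratory-rate threshold, and saturation is watched continuously.

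**Working it through.** **Inputs**
- Doses: Table 1 shows six per day for two days, and Section 4.3 packs twelve per kit. Nominal 4-hourly dosing puts them at 0, 4, ..., 44 h. Check: 48 / 4 = 12, which matches the kit.
- Scheduled blood pressure: 0, 1, 24, 25, 40, 41 and 48 h (7 sets).
- Time of mean peak concentration after a single dose: 0.27 to 0.60 h (Section 1.3).

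**Step 1: gaps.** 24 − 1 = 23 h; 40 − 25 = 15 h; 48 − 41 = 7 h. The ±10-minute windows change these only by minutes.

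**Step 2: doses given inside a gap**

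| Gap | Doses inside (h) | Count |
|---|---|---|
| 1–24 h | 4, 8, 12, 16, 20 | 5 |
| 25–40 h | 28, 32, 36 | 3 |
| 41–48 h | 44 | 1 |
| Total | | 9 of 12 |

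The first gap holds doses 2 to 6: 5 × 100 = 500 of 600 µg, or 5 × 200 = 1000 of 1200 µg, on the first day.

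**Step 3: doses with no later reading up to the time of the next dose.** A dose at time d is uncovered if no reading falls after d and by d + 4 h. The 20-h dose is followed by the 24-h reading, the 36-h dose by the 40-h reading and the 44-h dose by the 48-h reading. That leaves 9 − 3 = 6 of 12: the doses at 4, 8, 12, 16, 28 and 32 h.

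**Step 4: less frequent dosing.** Four hours is a minimum interval, so the counts shift if subjects take fewer doses.

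| Interval | Inside a gap | No later reading by the next dose |
|---|---|---|
| 4 h | 9 of 12 | 6 of 12 |
| 6 h, 40-h pair kept at 40 and 41 h | 6 of 8 (6, 12, 18, 30, 36, 42 h) | 3 of 8 (6, 12, 30 h) |
| 6 h, pair moved to the 36-h dose | 5 of 8 (6, 12, 18, 30, 42 h) | 2 of 8 (6, 12 h) |
| 6 h, pair moved to the 42-h dose | 5 of 8 (6, 12, 18, 30, 36 h) | 3 of 8 (6, 12, 30 h) |
| 8 h | 3 of 6 (8, 16, 32 h) | 1 of 6 (8 h) |

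**Step 5: effect of the proposed readings at 4-hourly dosing.** Nine pre-dose readings (4, 8, 12, 16, 20, 28, 32, 36, 44 h) and one at 1.5 h make 10 added, so 7 + 10 = 17 sets. Doses with a pre-dose reading go from 3 (0, 24, 40 h) to 12 of 12. The longest gap becomes 4 h. With 6-hourly dosing it would be 6 h, and with 8-hourly dosing 8 h.

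**Step 6: alternative timing.** Nine readings taken 1 h after each dose inside a gap (5, 9, 13, 17, 21, 29, 33, 37, 45 h) also give a longest gap of 4 h, and every dose then has a 1-h post-dose reading.

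**The case against.** The strongest reply is that nothing here is an error. The places that give the schedule agree, and item 4a says what to do when hypotension is found; it does not promise a reading before each dose. How often to measure blood pressure in a staffed inpatient unit is a judgement. The residual risk is also narrow: systolic pressure below 80 mm Hg with no symptoms, no hypoxia and no unscheduled reading, inside a gap. Subjects are ASA P1 or P2, unstable cardiac disease is excluded, and investigators may withdraw anyone for their own protection. Section 1.4 presents the doses as comfortably inside the safety range seen in the multiple-dose study, and Section 1.3 reports up to 400 µg every 4 hours as well tolerated. All of this stands and keeps the severity down. It does not remove the point, because Section 1.3 also says the analysis of that study is still under way, and no hypotension rate is given.

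A second reply is that pre-dose readings are badly timed, about 4 hours after the previous dose when the peak comes within the first hour. That also stands. Their merit is that they stop a further dose going to a subject who is hypotensive at that moment. Readings 1 hour after dosing are a legitimate alternative. A lighter option, blood pressure at the existing 90-minute and 12-hour contacts, cuts the longest first-day gap to 24 − 12 = 12 h but leaves the 15-h gap.

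A reader might infer from the 9 of 12 count that nine doses go unchecked until after the next dose, or that subjects are unmonitored for hypotension inside the gaps. The documents support neither. Three of the nine are followed by a scheduled reading in time, and symptomatic or hypoxic events remain covered.

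**Conclusion.** The point holds as a cheap safety improvement of low to moderate severity. The three gaps follow directly from the schedule. At nominal 4-hourly dosing, 9 of 12 doses fall inside a gap, and for 6 of 12 no scheduled reading by the time of the next dose could trigger item 4a. Both counts rest on that dosing assumption and shrink with less frequent dosing; the second falls to 1 of 6 at 8-hourly dosing. The number of events that would be missed cannot be estimated from the documents and is probably low. The primary analysis is not affected, and the plan does not contradict itself.

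**What to change.** **Readings.** In Protocol Sections 6.2.3 and 7.3.2 item 1, Table 2 footnote d and SAP Appendix 1 footnote d, add blood pressure immediately before every study-drug dose and at the existing 90-minute ECG/SpO2 contact. Where a pain rating is due, take the rating first, then the blood pressure, then give the dose.

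**Hold rule.** In Section 3.3 item 4a and Section 7.3.2 item 5 (and footnote l in both schedules, which repeats the dosing window), add:
- If pre-dose systolic pressure is below 80 mm Hg, hold the dose while three repeats are taken over 15 minutes.
- If all three are below 80 mm Hg, discontinue under item 4a.
- If not, give the dose only on the investigator's decision. It must not follow automatically, since two of three repeats could still be below the limit.
- If the subject is symptomatic, item 4b applies.
- The delay is not a dosing-window deviation.

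**Tables.** In SAP Section 8.2.9, tabulate the added times and each subject's lowest systolic pressure by arm, beside the number of readings per subject, because that number follows the number of doses taken. State that most added readings are about 4 hours after a dose and do not exclude a fall near the 0.27 to 0.60 h peak. If that matters more to the sponsor, take the nine readings 1 hour after the doses inside the gaps instead.

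**Cost at 4-hourly dosing.** About 10 added readings per subject (7 to 17 sets), or 10 × 45 = 450 over the trial if every subject takes all doses. The 5-minute rest adds 10 × 5 = 50 minutes per subject over 48 hours. Seven of the 10 fall at a scheduled pain rating (1.5, 4, 8, 12, 16, 20 and 32 h), which is why the order must be fixed. A held dose is delayed by at least 15 minutes. CRF fields and table rows are also needed. Staff already give each spray to a confined inpatient, so no visits or subjects are added.
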